### **8.1.3 Subgroup analysis of the primary variable retention at 12 months**

The analysis described in [Section 8.1.1](#) will be repeated for each of the subgroups described in [Section 4.8](#).

## **8.2 Statistical analysis of the secondary variables**

### **8.2.1 Retention at 3 and 6 months**

Similar to the primary endpoint, patients will be classed as having 3 months BRV retention if they do not meet either of the following criteria:

- Date of study termination < date of first BRV administration + 90 days
- Date of last administration of BRV while in the study < date of first BRV administration + 90 days

Otherwise, patients meeting either of the bulleted conditions above will be categorized as not having 3 months BRV retention. 90 days is selected because at least 3 months BRV retention is required, hence a patient who attends a month 3 visit early and terminates BRV prior to Day 90, would not be classed as having 3 months retention.

Patients will be classed as having 6 months BRV retention if they do not meet either of the following criteria:

- Date of study termination < date of first BRV administration + 180 days
- Date of last administration of BRV while in the study < date of first BRV administration + 180 days

Otherwise, patients meeting either of the bulleted conditions above will be categorized as not having 6 months BRV retention. 180 days is selected because at least 6 months BRV retention is required, hence a patient who attends a month 6 visit early and terminates BRV prior to Day 180 would not be classed as having 6 months retention.

BRV Retention at 3 and 6 months will be summarized using the methods described in [Section 8.1](#) for the FAS and the modified FAS. BRV Retention at 3 and 6 months will be listed as described in [Section 8.1.1](#).

### **8.2.2 Seizure frequency related variables**

#### **8.2.2.1 Initial processing of diary data**

The number of POS since the last visit will be reported at each visit and Month 12/ Withdrawal. The 28-day post-Baseline seizure frequency for POS will be calculated as:

---

$$\frac{\text{Number of POS recorded at visit}}{\text{(Date of visit – Date of previous visit)}} \times 28$$

(Date of visit – Date of previous visit)

Partial-onset seizures frequency will only be calculated at visits attended and with seizure data recorded. For seizure frequency summaries, data recorded at Visit 4 (Month 12/Withdrawal) visit will be mapped to the appropriate scheduled visits as described in [Section 3.2.2](#). No mapping will be performed for Seizure freedom as the derivation is date based rather than visit based.

Twenty eight-day Baseline POS frequency (28-day Baseline) will be calculated using the Historical Seizure Count CRF page, as the number of POS recorded during the 3 months prior to first BRV administration / 3. For all seizures and POS with secondary generalization, the 28-day Baseline will be calculated using the same method of dividing the number recorded during the 3 months prior to first BRV administration by 3.

If Visit 4 data are missing, then the Visit 4 (Month 12) and Visit 4 (Month 12/Withdrawal) seizure rates will be missing. Visit 4 (Month 12) and Visit 4 (Month 12/Withdrawal) will be derived according to [Section 3.2.2](#).

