### 5 STUDY DESIGN

EP0077 is a postmarketing, multinational, multicenter, prospective NIS conducted at approximately 100 sites in approximately 10 European countries, with a 12-month Observation Period. Brivaracetam will be prescribed according to normal clinical practice and in accordance with the current SmPC in Europe for BRV (BRV indicated as adjunctive therapy in the treatment of POS with or without secondary generalization in patients 16 years of age and older with epilepsy). It is planned to include 530 patients in the study (see [Section 12.4](#)).

The patients will be followed as per current clinical practice. No additional clinical diagnostic or monitoring procedures will be applied. The use of an epilepsy/seizure diary, as standard clinical practice, is a requirement to enter the study. The selected questionnaires will be used if part of the standard clinical practice at the sites for the management of patients with epilepsy. The choice of medical treatment is made independently by the treating physician in the regular course of practice and is not influenced by the NIS protocol.

All patients (and/or their parents or legal representatives) have to accept in writing that his/her medical data will be used for the evaluation of the study results by signing a study-specific Patient Data Consent form according to local requirements.

The clinical evaluation of patients with epilepsy will be performed by the treating physician following routine clinical practice. All visits and assessments will be scheduled and conducted per routine clinical practice. It is anticipated that each patient will have approximately 4 visits during their participation in this study. These visits will consist of:

- Visit 1, Baseline, Day 1: represents the first day of BRV treatment
- Visit 2, approximately 3 months after Baseline
- Visit 3, approximately 6 months after Baseline
- Visit 4, approximately 12 months after Baseline or end of Observation Period

For patients who discontinue early, the treating physician should collect data as specified for Visit 4 as a Withdrawal Visit. Information on seizures will be collected using patient epilepsy diaries. All data to be collected at Visits 1, 2, 3, and 4 are described in [Section 17](#), [Table 17-1](#).

At those visits, the information collected by the treating physician will include data from any additional visits that the patients may have performed in between.

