**Table 17–1: Recommended schedule of study assessments**

Assessments	Visit 1 a Baseline/Day 1 First Day of BRV Treatment	Visit 2 3 Months (Approximately 3 months after Baseline according to routine practice b )	Visit 3 6 Months (Approximately 6 months after Baseline according to routine practice b )	Visit 4 c 12 Months (Approximately 12 months after Baseline according to routine practice b ) End of Observation/ Withdrawal Visit
Recording of AEs	X h	X	X	X
QOLIE-31-P	X	X	X	X
EpiTrack cognition assessment	X		X	X
CGIC		X	X	X
PGIC		X	X	X
Withdrawal criteria		X	X	
Study termination				X

AE=adverse event; AED=antiepileptic drug; BRV=brivaracetam; CGIC=Clinical Global Impression of Change; PGIC= Patient’s Global Impression of Change; QOLIE-31-P=Patient Weighted Quality of Life in Epilepsy Inventory-Form 31

a Visit 1 will be performed after the decision is taken to start adjunctive BRV therapy. Treatment with BRV should be initiated according to routine clinical practice. If the first dose of BRV is given on the same day as Visit 1, it should be administered after Baseline assessments are complete.

b The frequency of visits after Visit 1 will be based on local clinical practice and the patients’ requirements. The clinical procedures performed at each visit will also follow local clinical practice.

c For patients who discontinue early, the treating physician should collect data as specified for Visit 4 as a Withdrawal Visit.

d To include year of first epilepsy diagnosis, lifetime AEDs, etiology. Dates of use of levetiracetam with dosages and reason for discontinuation will be recorded when applicable.

e The treating physician will explain the importance of diary completion to the patient and will review his/her diary at each visit.

f The treating physician will evaluate at each visit the frequency and type of seizures experienced by the patient since the previous study visit. At Baseline, seizure frequency will be based on the previous 3 months to estimate the frequency per 28 days.

g Record name of AED and dose, and any changes after Visit 1.

h Adverse events will be recorded from the moment data consent is obtained.

---

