### 8.2.2.2 Derivation of seizure frequency related variables

The following variables will be defined for each visit and Month 12 /Withdrawal using the 28-day Baseline and 28-day post-Baseline seizure frequency variables described in [Section 8.2.2.1](#).

- Absolute reduction in POS frequency defined as:  
$$28\text{-day Baseline} - 28\text{-day post-Baseline seizure frequency}$$
- Percent reduction in POS frequency defined as:  
$$\frac{28\text{-day Baseline} - 28\text{-day post-Baseline seizure frequency}}{28\text{-day Baseline}} \times 100$$
- Patients with 0 POS at Baseline will be excluded from the analysis of percent reduction and response ( $\geq 50\%$ ).
- Response (Yes, No) where Yes is  $\geq 50\%$  reduction in POS frequency calculated as described above and No otherwise.
- Seizure freedom (Yes, No) will be defined using 2 methods as shown in [Table 8-1](#). The first method considers patients who withdraw prior to their 1st seizure as Not seizure free. The 2nd is a less conservative method which considers patients who withdraw prior to their 1st seizure as missing. Visit 4 (Month 12/Withdrawal) will not be summarized for seizure freedom.

Table 8–1: Derivation of seizure freedom		
Patient Classification at Visit (patients are assigned to the first category they fall into)	Seizure freedom – Discontinuations counted as not seizure free	Seizure freedom – Discontinuations counted as missing
0. Patients had a seizure before 1st BRV dose	Missing	Missing
1. Patient had a seizure on or after 1st BRV dose and on or before the visit date derived using the following conditions. First_seizure_date = Date of first seizure or if date of first seizure is missing but patient has seizures recorded at a visit, then assign first_seizure_date as the date of the visit prior to the earliest visit with seizures recorded a) Visit date present and First_seizure_date is on or after 1st BRV and on or before the Visit date b) Visit date is missing (either due to patient ongoing in study or visit missed) and First_seizure_date is on or after 1st BRV and on or before the visits target day [a])	No	No
2. Patient discontinued BRV or terminated the study prior to the visit’s target day [a]	No	Missing

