**Table 8–2: Derivation of time to first seizure**

Missing date of first seizure but seizures recorded				No evidence of seizures on the study			
V2	V3	V4	Date used	V2	V3	V4	Date used
M	M	>0	E-V1/1BRV [a]	M	M	M	C-V1
M	>0	NA	E-V1/1BRV [a]	0	M	M	C-V2
>0	NA	NA	E-V1/1BRV	M	0	M	C-V1
0	>0	NA	E-V2	M	M	0	C-V1
0	0	>0	E-V3	0	0	M	C-V3
M	-	>0	E-V1/1BRV [a]	0	M	0	C-V2
0	-	>0	E-V2	M	0	0	C-V1
-	>0	NA	E-V1/1BRV [a]	0	0	0	C-V4
-	M	>0	E-V1/1BRV [a]	0	Disc BRV	NA	C- Last BRV
				M	Disc BRV	NA	C-V1

[a] The rationale behind using V1/1BRV in this scenario is based on it being unknown when exactly between V1 and V4 that the first seizure event occurred. V1/1BRV is more conservative and hence will be used, however a sensitivity analysis may be performed if there are a lot of patients with missing data.

Note: M=patient is missing seizure data at this visit but attended the visit, - = patient missed entire visit, NA=Visit is not applicable/not required to be considered in this scenario, V=Visit, C=Censor, E=Event, 1BRV= Date of first dose of BRV, Last BRV= date of last dose of BRV.

Note: V1/1BRV implies the date of the first dose of BRV should be used if it is later than V1 to avoid negative time to events and under-reporting of potential seizure events. For patients with no evidence of seizures on the study, negative censoring times are acceptable as it is equivalent to censoring the patient on Day 1.

The time to first seizure from the date of first dose of BRV will be analyzed using Kaplan-Meier methods, from which the median time to first seizure (and 95% CI) will be calculated, along with 25% and 75% quartiles (and 95% CI for the quartiles). In addition, the cumulative number of events, number at risk, and survival estimate at monthly intervals will be provided. The Kaplan-Meier plot and raw statistical procedure output will be produced for the Kaplan-Meier analysis. This will be performed on the FAS and the modified FAS.

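### The first post-Baseline seizure rate runs from Visit 1 rather than from first BRV, so untreated days enter the on-BRV rate for any patient whose first dose comes later

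*SAP*

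**What the plan says.** On the count of partial-onset seizures (POS), SAP 8.2.2.1 says: "The number of POS since the last visit will be reported at each visit and Month 12/ Withdrawal". It divides that count by ("Date of visit – Date of previous visit") and multiplies by 28. At Visit 2 the preceding visit is Visit 1. The Baseline in the same section is tied to the first dose instead; it is computed "as the number of POS recorded during the 3 months prior to first BRV administration / 3".

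On whether the two dates coincide, the documents point both ways:

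- Protocol section 5 has "Visit 1, Baseline, Day 1: represents the first day of BRV treatment". SAP 2.3 and the column heading of Table 17–1 agree.
- Footnote a of Table 17–1 says "Visit 1 will be performed after the decision is taken to start adjunctive BRV therapy", and then "If the first dose of BRV is given on the same day as Visit 1, it should be administered after Baseline assessments are complete". The same-day dose is conditional. No longest interval is given there, in the selection criteria (protocol 8.1) or in the SAP.
- SAP Table 8–1 opens with a category for patients whose seizure came before the first dose, and sets their seizure freedom to missing.
- The note to SAP Table 8–2 says "V1/1BRV implies the date of the first dose of BRV should be used if it is later than V1".

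No comparable rule exists for POS frequency, percent reduction or response.

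**The concern.** A patient seen at Visit 1 who takes the first tablet some days later contributes those days, and any seizures in them, to a rate that is reported as the rate on BRV. If untreated seizures occur at the Baseline rate, the mixture lies closer to Baseline than the treated rate does, and more so as the gap grows.

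Absolute reduction, percent reduction and response of at least 50% at 3 months are secondary variables serving the seizure-control objective. The error reaches the first post-Baseline interval only. That is normally Visit 2. It can also be an early withdrawal visit mapped to Visit 2 under SAP 3.2.2, or the next visit attended if Visit 2 was missed.

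**Working it through.** The documents state no figure for this rate, so there is none to reproduce. The check follows the SAP's formula through.

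**Inputs.** The rate, the Baseline and the 50% threshold come from SAP 8.2.2.1 and 8.2.2.2. Visit 2 is placed D = 90 days after Visit 1 (about 3 months in both documents; 90 is the SAP's target day). The gap g from Visit 1 to first BRV is not given, so a range is shown. The true reduction r on BRV is assumed, and seizures during the gap are assumed to occur at the Baseline rate.

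**Reduction read at Visit 2 against a true 28-day Baseline.** The expected rate is a weighted mean of untreated and treated time, so the reduction read is r × (1 − g/D).

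**Reduction read against the SAP's Baseline.** Three months is 365.25/4 = 91.3 days, but dividing by 3 treats it as three 28-day periods, 84 days. The Baseline is therefore 91.3/84 = 1.087 times the true 28-day rate. The reduction read is 1 − [1 − r(1 − g/D)]/1.087.

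With r = 50% and D = 90:

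| Gap (days) | True 28-day Baseline | SAP Baseline |
|---|---|---|
| 0 | 50.0% | 54.0% |
| 7 | 46.1% | 50.4% |
| 8 | 45.6% | 49.9% |
| 14 | 42.2% | 46.8% |
| 30 | 33.3% | 38.7% |

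**Where response is lost under the SAP's Baseline.** Response needs r(1 − g/90) ≥ 1 − 0.5 × 1.087 = 0.4565. A true reduction of exactly 50% fails from a gap of 8 days, 55% from 16, 60% from 22 and 70% from 32. If three months is counted as 90 days, the factor is 90/84 = 1.071 and the first of these moves to 7 days: 0.5 × 83/90 = 0.461, below 1 − 0.5 × 1.071 = 0.464.

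**A patient away from the threshold (assumed).** Take 26 POS in the three months before BRV, a true 55% reduction, a 21-day gap and Visit 2 at 90 days after the first dose.

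- SAP Baseline: 26/3 = 8.67.
- Expected POS: 6.0 in the gap and 11.5 on BRV.
- SAP rate: (6.0 + 11.5)/111 × 28 = 4.42, a 49.0% reduction, so non-response.
- Counted from first dose: 11.5/90 × 28 = 3.59, a 58.6% reduction, so response.

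**A short first interval (assumed).** Take withdrawal 30 days after first dose, mapped to Visit 2, with a 14-day gap and a true 60% reduction. This reads 0.60 × 30/44 = 40.9% against a true Baseline, or 1 − (1 − 0.409)/1.087 = 45.6% against the SAP's. Both are non-response.

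**The case against.** The strongest reply is that the gap is zero by design: both documents call Visit 1 the first day of treatment. These are also secondary, descriptive variables, and Visit 3 and Visit 4 rates are untouched when Visit 2 was attended. All of that stands, and it bounds the point. It does not remove it, because the SAP plans for a later first dose in two other seizure variables and leaves this one without a rule.

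A reader might infer more than the documents support:

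- *Every gap turns a 50% responder into a non-responder.* This holds only against a true 28-day Baseline. With the SAP's inflated one, a 7-day gap still reads 50.4%.
- *The net error always works against BRV.* For a borderline responder with a gap of up to about a week, the Baseline inflation outweighs the dilution.
- *Gap days are counted in both windows.* The wording of the two definitions permits this, but Table 17–1 has the Baseline seizure history documented at Visit 1. A count taken then cannot include later days. Double counting is not shown.
- *Local supply drives the gap.* The protocol links commercial availability to country start dates and site selection, not to when an individual patient begins.
- *Table 8–2 is a general correction to first dose.* Its floor applies to events whose first-seizure date is missing. For censored patients the same note accepts negative times.

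There is also a fair objection to a simple repair. SAP 4.2.1 has the physician enter a count since the previous visit, and protocol section 11 asks for seizure numbers only where possible. Not every count can be split at first BRV.

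**Conclusion.** The point holds in limited form. As written, SAP 8.2.2.1 counts untreated days as on-BRV time in the first post-Baseline rate of any patient with a gap between Visit 1 and first BRV, and no text limits that gap. For a true 50% reduction and Visit 2 at 90 days, the dilution alone costs about 4, 8 and 17 percentage points at 7, 14 and 30 days (50 − 46.1, 50 − 42.2, 50 − 33.3). Net of the Baseline inflation, an exact 50% responder is lost from a gap of about 8 days, and patients well above 50% need several weeks.

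These figures rest on the assumed visit day, constant seizure rates and assumed gaps. The effect on the study's Month 3 results cannot be stated, because the gap distribution is not in the documents; for same-day starters the gap effect is zero. Retention, the primary variable, is dated from first BRV and is not affected. The two errors do not reliably cancel: the Baseline inflation is a roughly constant factor, while the dilution varies by patient.

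**What to change.** In SAP 8.2.2.1:

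1. For the first post-Baseline interval, count only POS dated on or after first BRV, and divide by the visit date minus the later of the previous visit date and the first BRV date.
2. Where the count cannot be split at first BRV, keep the visit-to-visit interval for both numerator and denominator in the main table, and exclude those patients in a sensitivity table. Never pair an undivided count with the shortened denominator. With a Baseline of 8 per 28 days, 4 on BRV and a 30-day gap, that would give (30 × 8 + 60 × 4)/60 = 8, a 0% reduction, where the present formula gives 33.3% (both against a true 28-day Baseline).
3. Scale the Baseline count to 28 days by the actual length of the three-month window. Make this change together with the first: correcting the gap alone leaves a true 50% reduction reading 54.0%.
4. Report the distribution of the interval from Visit 1 to first BRV.

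The cost is SAP wording and a small programming change. Visit dates and the first BRV date are already derived, and Table 17–1 lists seizure date among the items documented. Some patients without dated seizures drop out of the sensitivity table; how many cannot be judged from the documents.

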### 3.2.2 Visit 4, Month 12/Withdrawal Visit

Patients with early study termination (ie, those who complete the Study Termination [Dropout] CRF page), will have their Visit 4 (Month 12/Withdrawal) visits prior to the preferred visit window for Month 12 of greater than or equal to 330 days after date of first BRV administration. Patients completing the study (ie, those who complete the Study Termination NIS [Completed Subject] CRF form), will have their Visit 4 (Month 12/Withdrawal) visits within the preferred visit window for Month 12 of greater than or equal to 330 days after date of first BRV administration. Therefore, Visit 4 will be analyzed as follows depending on the objective and variable being analyzed:

- Visit 4 (Month 12): Including only patients who are study completers with a Visit 4 within the preferred visit window for Month 12 of greater than or equal to 330 days after the date of first BRV administration.
- Visit 4 (Month 12/Withdrawal): Including all data recorded at Visit 4 (ie, completers or patients who withdraw early)

In addition, Visit 4 (Month 12/Withdrawal) visits that correspond to scheduled visits will be included in the counts for the scheduled visits to which they correspond. To be classed as corresponding to the scheduled visit, the withdrawal visit must fall into the windows provided below and the patient have no scheduled visit already available. Only the variables below will have the mapping of withdrawal visits applied.

Variables	Visit 2, Month 3	Visit 3, Month 6
Disposition (Patients attending each visit)	30-135	136-329
Seizure Frequency	30-135	136-329
QOLIE	30-135	136-329
CGIC/PGIC	30-135	136-329
EpiTrack	No mapping as no scheduled visit	150-210

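### With no minimum interval behind the Visit 4 (Month 12/Withdrawal) POS rate, a withdrawal visit soon after Visit 2 or 3 gives a ≥50% response result that mainly reflects interval length

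*SAP*

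**What the plan says.** - **Numerator** (SAP 8.2.2.1): "The number of POS since the last visit will be reported at each visit and Month 12/ Withdrawal".
- **Denominator** (SAP 8.2.2.1): "Date of visit – Date of previous visit", with the quotient multiplied by 28.
- **Condition for a rate** (SAP 8.2.2.1): "Partial-onset seizures frequency will only be calculated at visits attended and with seizure data recorded". Interval length is not mentioned.
- **Baseline rate** (SAP 8.2.2.1): calculated "as the number of POS recorded during the 3 months prior to first BRV administration / 3".
- **Response** (SAP 8.2.2.2): Yes for a fall of at least 50%, "reduction in POS frequency calculated as described above and No otherwise". The one exclusion is: "Patients with 0 POS at Baseline will be excluded from the analysis of percent reduction and response".
- **Who is counted at Visit 4 (Month 12/Withdrawal)** (SAP 3.2.2): "Including all data recorded at Visit 4 (ie, completers or patients who withdraw early". Visit 4 (Month 12) is limited to completers seen at 330 days or later.
- **Mapping to Month 3 or Month 6** (SAP 3.2.2): "the withdrawal visit must fall into the windows provided below and the patient have no scheduled visit already available". The windows, Days 30-135 and 136-329, set the position of the visit, not the time since the visit before it.

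Visits follow routine practice, and early discontinuation triggers a withdrawal visit (Protocol Section 5). Responders are tabulated at Visit 4 (Month 12/Withdrawal), and the responder analysis is repeated in patients who stopped for lack of efficacy (SAP 4.6 and 8.2.2.3).

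**The concern.** A rate taken over a few days carries almost no information about a patient who has one or two seizures a month. Zero seizures is then the likely count whatever the drug does, and zero is scored as a 100% reduction. The diary data already reported at Visit 2 or 3 play no part in the result.

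The response and the reductions at the end of the Observation Period are secondary variables for the seizure-control objective. Visit 4 (Month 12) contains completers only, and SAP 3.9 drops seizure freedom at the end of the Observation Period. The POS reductions and response are therefore the only seizure-control summaries left at that time point that include withdrawals.

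The SAP also treats comparable patients differently. Table 8-1 counts someone who stops before a visit's target day without a seizure as not seizure free (method 1) or missing (method 2). The responder rule counts a seizure-free last few days as success.

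**Working it through.** The documents state no responder rate, so there is no figure of this kind to reproduce. The sample-size figure does reproduce (1.96² × 0.25 / 0.05² = 385) but is used here only to convert shares into patients.

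**The rule.** With Baseline count X over 3 months, count Y since the previous visit, and d days in between, response is Yes if 28Y/d ≤ 0.5 × X/3.

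**One patient.** X = 3 gives a Baseline rate of 1.0. At d = 7, Y = 0 gives a 100% reduction. Y = 1 gives 28 × 1/7 = 4.0 and (1 − 4)/1 × 100 = −300%. At d = 0 the rate is undefined, and no rule covers it.

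**Unchanged rate.** Assumptions: Poisson counts, the same true rate before and after, X ≥ 1, and an 84-day Baseline so that X/3 is exactly a 28-day rate. At d = 7, a patient with any seizure can respond only if X ≥ 24, so the chance of response is in effect the chance of a zero count: exp(−7/28) = 0.78 at 1 per 28 days and exp(−14/28) = 0.61 at 2. Full enumeration over X and Y gives:

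| True rate per 28 days | 7 days | 14 days | 21 days | 91 days |
|---|---|---|---|---|
| 1 | 78% | 61% | 48% | 24% |
| 2 | 61% | 38% | 31% | 12% |
| 4 | 37% | 28% | 22% | 5% |

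With a 91.3-day Baseline the 7-day values at 1 and 2 per 28 days do not change, and the values at 90 days become 27% and 15%. If the rate doubles from 1 to 2 per 28 days, a 7-day interval still gives 61% responders. Overdispersion does not remove the effect: with a negative binomial of size 1, the chance of no seizure in 7 days at 1 per 28 days is 80%.

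**How many patients.** Assume dropout uniform over Days 1-329, visits at Days 91 and 182, and every dropout attending a withdrawal visit with seizure data.

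- Last interval of 1-27 days after Visit 2 or 3: 54/329 = 16%.
- Withdrawal on Days 1-27, with no earlier post-Baseline diary: 27/329 = 8%.
- At 385 patients and 50% retention (192.5 dropouts), these are about 32 and 16 patients.

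**Effect at 1 per 28 days, unchanged rate.**

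- Dropouts with at least 28 days of post-Baseline diary: 33.2% responders as written, 25.7% with pooling.
- Those whose short interval is pooled: 63% as written, 21% with pooling.
- Overall, 50% retention: completers respond in 16.8% (183 days, Day 182 to 365) and all dropouts in 35.7% as written. As written: 0.5 × 0.168 + 0.5 × 0.357 = 26.2%. With the fix: (0.5 × 0.168 + 0.459 × 0.257)/0.959 = 21%, where 0.459 = 0.5 × 0.918 is the evaluable dropouts.
- Overall, 70% retention: 0.7 × 0.168 + 0.3 × 0.357 = 22.5% as written, and (0.7 × 0.168 + 0.2754 × 0.257)/0.9754 = 19.3% with the fix.

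Part of each fall comes from the earliest dropouts leaving the denominator. On the same evaluable patients the contrasts are (0.084 + 0.459 × 0.332)/0.959 = 24.7% against 21.1%, and (0.1176 + 0.2754 × 0.332)/0.9754 = 21.4% against 19.3%.

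**Other assumptions.** With 30-50% withdrawing, 5-30% of them within 5 days of the previous visit, and rates of 1/3 to 2 per 28 days, replacing the 5-day interval with 95 days lowers the overall rate by about 0.7 to 9 points.

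**The case against.** The strongest objection concerns reach. Mapping requires that the scheduled visit be absent. With visits near Days 91 and 182, a withdrawal just after Visit 2 is mapped neither to Month 3 (Visit 2 exists) nor to Month 6 (before Day 136). Mapped intervals are then about 30 days or more for Month 3 and 45 or more for Month 6. A short mapped interval needs something like a Visit 2 on Day 130, a withdrawal on Day 136 and no Visit 3. This stands: a reader might infer that Months 3 and 6 share the problem, but with on-time visits they largely do not.

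The second concerns direction. A reader might infer that treatment failures are systematically turned into responders, above all in the lack-of-efficacy subset. The documents do not support that. The calculation takes the last-interval count as independent of the decision to withdraw. A patient leaving for lack of effect may come in because of recent seizures, and one seizure on a short interval makes a non-responder with an extreme negative reduction. The net direction in that subset is unknown.

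The third concerns size. Withdrawals within 7 days after Visit 2 or 3 are 14/329, about 4% of dropouts in this scenario, or roughly 8 of 193. The 50% retention figure was chosen for interval width and is not evidence on dropout. This also stands, and it is why the overall shift is a few points.

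Lastly, the analyses are descriptive, the primary variable is untouched, completers are shown separately, and the listing in SAP 8.2.2.3 shows days since the last visit. These let a reader notice short intervals, but they do not correct the tabulated Month 12/Withdrawal rate.

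**Conclusion.** Wrong as written for Visit 4 (Month 12/Withdrawal) and for the lack-of-efficacy subset. On a short last interval, response depends more on the number of days than on seizure control: 78% at 7 days against 24% at 91 days with no change at 1 POS per 28 days, and 61% against 12% at 2. The absolute and percent reductions are unstable in both directions, and a same-day visit has no defined rate.

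The statement that most patients respond by chance applies to infrequent seizures. On a 7-day interval a zero count is more likely than not only below 28 × ln 2 / 7 = 2.8 POS per 28 days. Visit 4 (Month 12) is largely unaffected, and Months 3 and 6 are affected only when a scheduled visit is late or missing.

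Under uniform dropout, the overall Month 12/Withdrawal responder rate is about 3 points (70% retention) to 5 points (50% retention) higher as written than with the fix. This rests on assumed dropout timing, Baseline rates, Poisson counts and full attendance at withdrawal visits, none of which the documents give.

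**What to change.** Add to SAP 8.2.2.1: if a Visit 4 (Month 12/Withdrawal) visit falls fewer than 28 days after the previous visit with seizure data, add the count and days of the whole preceding post-Baseline interval(s) until at least 28 days are covered, and calculate the rate as total count / total days × 28. If total post-Baseline diary time is under 28 days, calculate no rate and show the patient in a separate not-evaluable row. Apply this to absolute reduction, percent reduction and response, and footnote the numbers pooled and not evaluable. This also settles the same-day visit.

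The 28-day threshold is a choice, taken from the plan's own reporting unit. A bare 28-day minimum would help only partly, since null response at exactly 28 days is still about 40% at 1 per 28 days. Adding the whole preceding interval does more, because in the scenario above the pooled rate rests on at least 92 days.

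The cost is a few sentences and a small programming change, using counts and dates already collected. For pooled patients the rate includes time before the last scheduled visit, and a few very early withdrawals have no rate.
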